6.1. General Considerations

Statistical analysis of this study will be the responsibility of Eli Lilly and Company (hereafter Lilly) or its designee. Any change to the data analysis methods described in the protocol will require an amendment ONLY if it changes a principal feature of the protocol. Any other change to the data analysis methods described in the protocol, and the justification for making the change, will be described in the SAP or the clinical study report (CSR). Additional exploratory analyses of data will be conducted, as deemed appropriate.

For purposes of analysis, the following populations are defined in [Table ITRO 6.1](#).

Table ITRO 6.1. Patient Populations

Population	Description
Entered	All patients who give informed consent.
Enrolled	All patients who receive at least 1 dose of open-label Humalog in the 2-week lead-in period.
Randomized	All patients who are randomly assigned to study treatment at Visit 4. Treatment group will be defined based on the treatment the patients are assigned.
Safety	All randomized patients who receive at least 1 dose of the randomly assigned IP. Treatment group will be defined based on the treatment the patients were assigned.

Abbreviations: IP = investigational product.

Unless otherwise stated, the efficacy analyses will be conducted on the Randomized Population and the safety analyses will be conducted on the Safety Population.

The primary analysis is for the treatment period up through Week 16.

Unless otherwise noted, all tests of treatment effects will be conducted at a 2-sided alpha level of 0.05, and CIs will be calculated at 95%, 2-sided. All tests of interactions between treatment groups and other factors will be conducted at a 2-sided alpha level of 0.10.

The definitions of baseline and post-baseline for the efficacy and safety analyses depend on which analysis period is being used. The following analysis periods will be used:

- Lead-in Period – Visits 2 to 4
- 16-Week Treatment Period – from randomization to Week 16 prior to discontinuation of IP and from randomization to Week 16 (including all data regardless of IP use)
- 16-Week Treatment Period and Safety Follow-Up Visit – from randomization to Visit 801 (including all data regardless of IP use)

The data on IP is defined based on the following rules:

- For data only measured at an office visit
 - MMTT postbaseline data will be classified as on IP if the MMTT performance date is prior to or on the last IP dose date

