Health outcomes: ITSQ, EQ-5D-5L, EQ-VAS	All Randomized Patients with a baseline and a post-baseline observation	Last of Visits 2-4 prior to initiation of IP	Last of Visits 5-13 prior to discontinuation of IP
Safety Laboratory Tests (chemistry, hematology) – continuous analysis	All Patients in the Safety Population with a baseline and a post-baseline observation	Visit 1	Visit 13 (planned) AND last of Visits 5-13 (planned including early discontinuation visits) regardless of IP use
Safety Laboratory Tests (chemistry, hematology) – categorical analysis	All Patients in the Safety Population with a normal baseline (with respect to the direction being analyzed) and a post-baseline observation	Visits 1-4 (including unplanned tests)	Visits 5-13 (including unplanned tests) regardless of IP use
TEAEs	All Patients in the Safety Population	Prior to first dose of randomized IP (or Visit 4 date if the dose date is missing) but after the first dose of open-label insulin lispro in the Lead-in Period	From first dose of randomized IP to last dose of randomized IP AND From first dose of randomized IP to Visit 801
Hypoglycemia events	Safety Population	All Visits 2-4	All Visits 5-13 prior to discontinuation of IP
Unplanned infusion set changes	Safety Population	All Visits 2-4	All Visits 5-13 prior to discontinuation of IP
Weight and vital signs	All Patients in the Safety Population	Last of Visits 2-4	Visits 5-13 prior to discontinuation of IP

	with a baseline and a post-baseline observation		
Anti-insulin lispro antibodies	Safety Population	Visit 4	Visits 5-801 regardless of IP use

Abbreviations: 1,5-AG = 1,5-Anhydroglucitol; AIT = active insulin time; ANCOVA = analysis of covariance; CR = carbohydrate ratio; EQ-5D-5L = European Quality of Life – 5 Dimensions 5 Level; EQ-VAS = EuroQol visual analogue scale; HbA1c = hemoglobin A1c; IP = investigational product; ISF = insulin sensitivity factor; ITSQ = Insulin Treatment Satisfaction Questionnaire; ITT = intention-to-treat; LOCF – last-observation-carried forward; MMTT = mixed meal tolerance test; MMRM = mixed-effect model repeated measures; PPG = postprandial glucose; SMBG = self-monitored blood glucose; TEAE = treatment-emergent adverse event.

¹ If the percentage of the patients with missing MMTT data at baseline is higher than 15%, a constrained longitudinal data analysis model (Liu et al. 2009; Lu 2010) will be used instead. See Section 6.11.2.

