6.12.7. Immunogenicity

Blood samples for immunogenicity testing will be collected to determine antibody production against insulin lispro for all enrolled patients since Visit 4 prior to the first dose of study-provided prandial insulin treatment. Therefore, the blood sample result at Visit 4 will be considered as the anti-insulin lispro level at baseline for this study. The assessment of immunogenicity will include analyses of treatment-emergent anti-insulin lispro antibody up to Visit 801.

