6.12.7.1. Treatment Emergent Anti-Insulin Lispro Antibody

The treatment-emergent anti-insulin lispro antibody (denoted as treatment-emergent antidrug antibody [TEADA] throughout this SAP) is based on the change from baseline (Visit 4) to post-baseline (post-Visit 4) in the anti-insulin lispro antibody level (percent binding). Treatment-emergent antidrug antibody can be sub-classified as either treatment-induced (not detected anti-insulin lispro antibody at baseline) or treatment-boosted (detected anti-insulin antibody at baseline):

- treatment-induced response: change from not detected anti-insulin lispro at baseline (Visit 4) to post-baseline detected anti-insulin lispro;
- treatment-boosted response: change from detected anti-insulin lispro at baseline (Visit 4) to post-baseline detected anti-insulin lispro antibody level (percent binding) at least 157% of the baseline value.

The TEADA status during the analysis period will be determined using all data in the corresponding analysis period regardless of IP use. The summary for TEADA status and the anti-insulin lispro antibody level will use the same analysis data.

The number and percentage of patients with positive TEADA response at Visit 4, Visit 13 and Visit 801 will be summarized by treatment group. For patients with positive TEADA response, the number and percentage of patients with positive insulin cross-reactivity will also be summarized by treatment group. Treatment groups will be compared by Fisher’s exact test.

Both actual and change from baseline (Visit 4) for the anti-insulin lispro antibody level in percent binding will be summarized by scheduled visit prespecified in the protocol for patients with positive TEADA response from Visit 4 to Visit 801. The repeated measurement from Visit 4 to Visit 801 will be analyzed by an MMRM model with treatment, baseline value of the response variable, visit, and visit by treatment interaction as fixed factors and patient as the random factor. The ANCOVA model using treatment and baseline value as covariates will be

used for the analysis of last non-missing observation prior to or at Visit 801 and the analysis of maximum percent binding during the analysis period of Visit 4 to Visit 801.

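### SAP 6.12.7.1 makes Visit 4 both a response and the baseline covariate in the antibody MMRM, against Table ITRO 6.2; taken literally with one pooled variance, the Visit 13 and 801 contrasts test at about 8–12% instead of 5%

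*SAP*

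**What the plan says.** SAP 6.12.7 fixes the baseline: "the blood sample result at Visit 4 will be considered as the anti-insulin lispro level at baseline for this study".

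SAP 6.12.7.1 then specifies the model for percent binding, for both actual values and change from baseline: "The repeated measurement from Visit 4 to Visit 801 will be analyzed by an MMRM model with treatment, baseline value of the response variable". The full list of terms is "treatment, baseline value of the response variable, visit, and visit by treatment interaction as fixed factors and patient as the random factor". The section does not name a residual covariance structure. The visits it reports are 4, 13 and 801.

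Two other places point to post-baseline responses only:

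- **SAP Table ITRO 6.2** (in Section 6.1) gives Visit 4 as the antibody baseline and, in the post-baseline column, "Visits 5-801 regardless of IP use".
- **Protocol 10.3.1**, the general MMRM description, takes the observations at scheduled post-baseline visits. It names an unstructured covariance, with a list of fallback structures.

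Unless otherwise noted, SAP 6.1 says that "all tests of treatment effects will be conducted at a 2-sided alpha level of 0.05".

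**The concern.** Under the sentence as written, the Visit 4 record enters the response vector and the same number is the covariate. For change from baseline, every Visit 4 response is exactly zero. These rows carry almost no residual variation. A model with one variance common to all visits averages that small variation with the real variation at Visits 13 and 801, so the standard errors of the later contrasts are too small.

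At stake is a false between-arm difference in antibody level in the immunogenicity section, which would then need explaining.

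**Working it through.** The plan states no error rate, variance or power for this model, so there is no figure of its own to reproduce. The benchmark is the nominal two-sided 0.05.

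**Inputs from the documents:** 1:1 allocation; response visits 4, 13 and 801 if read literally, or 13 and 801 if post-baseline only; Visit 4 as covariate; patient as random factor.

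**Assumptions, not in the documents:** the random factor is an intercept with one pooled variance; correlation rho between baseline and later visits from 0 to 0.95; post-baseline SD 0.7 to 2 times the baseline SD; 30 to 184 patients per arm (184 is the planned number of completers per arm; the antibody-positive number is not given); complete data.

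**1. Large-sample formula, equal variances scaled to 1.** The covariate does not vary over visits, so one slope is fitted. It averages the visit slopes 1, rho and rho:

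- b = (1 + 2·rho)/3
- true residual variance at Visit 13 or 801 = (rho − b)² + 1 − rho²
- residual variance at Visit 4 = (1 − b)²
- variance the model uses = [(1 − b)² + 2·true]/3
- actual alpha = 2·[1 − Φ(1.96/√(true/model))]

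Example, rho = 0.7: b = 2.4/3 = 0.8; true = 0.01 + 0.51 = 0.52; Visit 4 = 0.04; model = (0.04 + 1.04)/3 = 0.36; ratio = 1.444; alpha = 2·[1 − Φ(1.96/1.202)] = 10.3%.

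| rho | true | model | ratio | alpha |
|---|---|---|---|---|
| 0 | 1.111 | 0.889 | 1.25 | 8.0% |
| 0.3 | 0.964 | 0.716 | 1.35 | 9.1% |
| 0.5 | 0.778 | 0.556 | 1.40 | 9.8% |
| 0.7 | 0.520 | 0.360 | 1.44 | 10.3% |
| 0.9 | 0.191 | 0.129 | 1.48 | 10.8% |

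The Visit 4 term cannot be negative, so with equal post-baseline variances the ratio cannot exceed 3/2. The ceiling is 11.0%. Ratios of 1.25 to 1.5 mean standard errors too small by 1 − 1/√1.25 = 11% to 1 − 1/√1.5 = 18%. Using change as the response lowers the slope by 1 and leaves the residuals unchanged, so the result is the same.

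**2. Null simulation, random-intercept REML, 6000 trials per setting, Visit 13 contrast.**

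| Setting | Visit 4 as response | Post-baseline only |
|---|---|---|
| Equal variances, rho 0.3 to 0.9, 30 to 184 per arm | 9.3–10.4% | 4.7–5.2% |
| Lognormal data | 10.0% | 4.8% |
| Post-baseline SD ratio 0.7 | 7.7% | 5.0% |
| Post-baseline SD ratio 1.5 | 11.8% | 5.7% |
| Post-baseline SD ratio 2 | 11.1% | 4.9% |

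The simulation standard error at 11.8% is √(0.118·0.882/6000), about 0.4 points.

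**3. Other tests in the same literal fits.** The treatment main effect rejects in 4.4–5.3% of trials and the treatment-by-visit interaction in 4.6–7.0%. The main effect keeps its size but averages in a Visit 4 difference that has no post-randomization content.

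**4. Other covariance structures.**

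- Homogeneous Toeplitz, one of the protocol's fallbacks (800 trials per setting): 9.4–12.9% for the visit contrasts.
- Unstructured: with slope 1 the Visit 4 residual vanishes and the likelihood has no maximum. With the Visit 4 residual SD set to 0.3, 0.1, 0.01, 0.001 and 0.0001, the REML log-likelihood was 189, 404, 857, 1311 and 1764. In the limit the Visit 13 test becomes an unadjusted change-score comparison, which rejected in 5.1–6.6% (simulation error about 0.8 points).

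**5. Maximum percent binding ANCOVA.** In 5000 null trials per setting (60 or 120 patients in total; rho 0.3, 0.7 or 0.9; normal and lognormal data), rejection was 4.1–4.9% with Visit 4 in the maximum and 4.3–5.1% without. There is no inflation.

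**The case against.** The strongest answer is that the plan already excludes Visit 4 as a response. Table ITRO 6.2 is introduced as the rule for baseline and post-baseline observations. Protocol 10.3.1 limits MMRM responses to post-baseline visits. SAP 6.12.7.1 itself defines post-baseline as after Visit 4, and elsewhere uses the same span as the label of a period, as in "maximum percent binding during the analysis period of Visit 4 to Visit 801". On that reading the sentence is only loosely worded.

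Much of this stands. A reader might infer that the plan definitely fits Visit 4 on both sides of the model; the documents do not settle that. They contradict each other, and the table and protocol probably show the intent. The sentence still needs correcting. The same section asks for treatment-emergent antibody counts at Visit 4, where no change from Visit 4 can exist, so it does list Visit 4 among the visits analysed. Nor can the model be read as a constrained longitudinal analysis, which may take baseline as a response: where SAP 6.13 specifies that method, it lists no baseline covariate.

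A reader might also infer that the maximum percent binding ANCOVA shares the fault, because its period starts at Visit 4. It does not. It has one response per patient, so no Visit 4 rows can shrink a pooled variance. If it is confined to patients with a treatment-emergent response, their maximum is post-baseline anyway: either the baseline was undetected or a later value is at least 157% of it.

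**Conclusion.** The point holds as a contradiction between the model sentence in SAP 6.12.7.1 and both Table ITRO 6.2 and protocol 10.3.1. It has a definite cost if the sentence is followed. With a random patient intercept and one pooled variance, the Visit 13 and 801 contrasts run at about 8–12% instead of 5%, under the assumed correlations and SD ratios.

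A reader might take this as a doubled false-positive rate for the antibody comparison in general. That goes too far. The treatment main effect stays near 5%, the interaction is near 5% in most settings, and under an unstructured covariance the failure is a degenerate fit rather than a doubled error rate.

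The matter is minor. Percent binding is a supporting analysis of an exploratory safety objective, outside the multiplicity scheme. The antibody endpoint itself is incidence, compared by Fisher's exact test, and is untouched, as are the primary and multiplicity-adjusted conclusions.

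**What to change.** In SAP 6.12.7.1, state that the MMRM responses are the visits after Visit 4 (Visits 13 and 801), with Visit 4 only as the covariate, in line with Table ITRO 6.2. Name the covariance structure and say whether the random patient factor replaces or accompanies it. The maximum percent binding ANCOVA needs no change on error-rate grounds.

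The cost is a few words in the SAP, with no new data and no change to study conduct. In the simulations, post-baseline responses brought the Visit 13 contrast back to 4.7–5.7%.

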9.8. Immunogenicity Testing

Blood samples for immunogenicity testing will be collected to determine antibody production against insulin lispro as specified in the Schedule of Activities (Section 2, Table ITRO.1).

Immunogenicity will be assessed by a validated radio ligand-binding assay (RBA) to detect anti-insulin lispro antibodies in the presence of lispro. Instead of quantitating the level of anti-insulin lispro antibodies by titer, the RBA reports a semiquantitative percent-binding for each positive sample. Additionally, positive samples will be characterized for cross-reactive binding to native insulin.

Clinical and reliable on-market data indicate that the immunogenic potential of insulin lispro is comparable to other marketed insulins such as regular human insulin (Fineberg et al. 1996) and, when present, anti-insulin antibodies do not appear to be clinically consequential (Fineberg et al. 2003). Therefore, rather than relying on an in vitro neutralization assay, well established in vivo measures of insulin lispro efficacy (that is, insulin dose, HbA1c) will be utilized to directly monitor for any potential neutralizing effect of anti-lispro antibodies.

Samples will be retained for a maximum of 15 years after the last patient visit for the study, or for a shorter period if regulations and ERBs impose shorter time limits, at a facility selected by Lilly or its designee. The duration allows the sponsor to respond to future regulatory requests related to LY900014.

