A listing of anti-insulin lispro antibody at each visit will be provided. The listing will include anti-insulin lispro antibody status (detected/not detected), anti-insulin lispro antibody percent binding, TEADA status (positive/negative), insulin cross-reactivity status, and insulin cross-reactivity percent binding for the safety population.

Subgroup analysis for the following selected efficacy and safety variables will be performed by the TEADA status during the analysis period of Visit 4 to Visit 801:

- HbA1c and change from baseline in HbA1c
- 1-hour and 2-hour PPG
- basal, prandial, and total insulin dose
- treatment-emergent infusion site reaction and hypersensitivity reaction
- event rate of all documented hypoglycemic events

The analyses for HbA1c and change from baseline in HbA1c will be performed using an MMRM model for the primary analysis and the HbA1c data prior to permanent discontinuation of IP. The model will include additional fixed terms of subgroup, subgroup by treatment interaction, subgroup by visit interaction, and 3-way interaction of treatment, subgroup and visit.

The PPG will be analyzed by the ANCOVA model same as the model specified in Section 6.11.2 using the efficacy estimand. The model will include additional terms of subgroup, subgroup by treatment interaction, subgroup by visit interaction, and 3-way interaction of treatment, subgroup and visit.

The subgroup analysis for insulin dose will use the MMRM model specified in Section 6.11.4 using the efficacy estimand. The model will include additional fixed terms of subgroup, subgroup by treatment interaction, subgroup by visit interaction, and 3-way interaction of treatment, subgroup and visit.

The treatment-emergent infusion site reaction and hypersensitivity reaction will be analyzed by a logistic regression model including terms of treatment, subgroup, treatment by subgroup interaction. All data regardless of IP use will be used for this analysis.

The negative binomial regression model with treatment with additional terms of subgroup, treatment by subgroup interaction will be used for the subgroup analysis of all documented hypoglycemia event rate while on IP.

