The interaction effects (3-way for MMRM and 2-way for ANCOVA/logistic regression model/negative binomial regression model) will be evaluated using a significance level of 0.10, unadjusted. If the interaction effect is significant ($p < 0.10$), separate analysis without the terms related with the subgroup will be performed for each subpopulation.

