6.14. Subgroup Analyses

6.14.1. Subgroup Analyses for HbA1c

The following subgroups will be analyzed using the efficacy estimand to evaluate consistency of treatment effects on the primary efficacy measure if there are sufficient numbers of patients in each treatment by subgroup (10% in each subgroup level):

- Age (<40 years, ≥ 40 years)
- HbA1c stratum ($\leq 7.5\%$, $> 7.5\%$)
- Patient's personal CGM/FGM use during the study (yes/no)
- Sex (Male or Female)
- BMI (using the median as the cutoff)
- Bolus delivery speed at study entry
- Use of low glucose suspend
- Duration of diabetes (using the median as the cutoff)
- Duration of CSII use (using the median as the cutoff)
- Race
- Ethnicity
- Country
- Region
- Pump model series (500 Series [MiniMed 530G, MiniMed Paradigm Revel, MiniMed Paradigm Veo], 600 Series [MiniMed 630G, MiniMed 640G])

Analyses for HbA1c and change from baseline in HbA1c will be performed using an MMRM model that includes the same fixed effects given for the primary analysis model plus factors of subgroup, 2-way interaction of subgroup and treatment, 2-way interaction of subgroup and visit, and 3-way interaction of treatment, visit and subgroup. The interaction of subgroup and treatment at the primary endpoint (Week 16) will be evaluated to assess the treatment by subgroup interaction. When analyzing HbA1c stratum ($\leq 7.5\%$, $> 7.5\%$) as a subgroup the baseline HbA1c will be not be included as a covariate to avoid confounding.

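### For HbA1c and insulin dose by antibody status, the SAP evaluates only the treatment-by-TEADA-by-visit term, which cannot detect an effect that is constant over visits or shared by both lispro arms

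*SAP*

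**What the plan says.** - **Role of the two measures.** Protocol 9.8 does without a laboratory test of neutralization and relies on clinical measures instead: "well established in vivo measures of insulin lispro efficacy (that is, insulin dose, HbA1c) will be utilized to directly monitor for any potential neutralizing effect".
- **Models.** SAP 6.12.7.1 analyses several outcomes by TEADA status. For HbA1c: "The analyses for HbA1c and change from baseline in HbA1c will be performed using an MMRM model for the primary analysis". For dose: "The subgroup analysis for insulin dose will use the MMRM model specified in Section 6.11.4 using the efficacy estimand". To each MMRM it adds TEADA, TEADA-by-treatment, "subgroup by visit interaction, and 3-way interaction of treatment, subgroup and visit".
- **What is evaluated.** "The interaction effects (3-way for MMRM and 2-way for ANCOVA/logistic regression model/negative binomial regression model) will be evaluated using a significance level of 0.10". Only if p<0.10 are separate analyses run in each TEADA subpopulation, and these omit the TEADA terms.
- **Visits analysed.** SAP Table ITRO 6.2 gives Visits 8, 10 and 13 (Weeks 4, 8 and 16) for HbA1c, and Visits 6, 8, 10 and 13 for insulin dose. All are post-baseline.
- **Definition of status.** The subgroup analyses "will be performed by the TEADA status during the analysis period of Visit 4 to Visit 801".
- **Practice elsewhere.** For the other HbA1c subgroups, SAP 6.14.1 adds the same kinds of term but states: "The interaction of subgroup and treatment at the primary endpoint (Week 16) will be evaluated to assess the treatment by subgroup interaction".

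**The concern.** Both arms infuse insulin lispro. If antibodies blunt its action, TEADA-positive patients should show higher HbA1c, a higher dose, or both, compared with TEADA-negative patients. This could happen in both arms or more in one. The term chosen for HbA1c and dose addresses neither directly, because it asks whether the difference between arms in the TEADA effect changes from visit to visit. If that difference is present and flat, or if the TEADA effect is the same in both arms, the term is zero however large the effect.

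The follow-up step does not repair this. The separate analyses compare treatments within a TEADA subpopulation and never compare positive with negative patients. At stake is how a null result is read: a non-significant 3-way p-value could be reported as no sign of neutralization in situations where the test could not have shown one.

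**Working it through.** **The plan's own figures.** SAP 5.2 gives 184 completers per arm, SD 0.88% and no true difference. SE = 0.88 x sqrt(2/184) = 0.0917. Power at margin 0.4% = Phi(0.4/0.0917 - 1.96) = 99.2%; at 0.3% it is 90.5%. Both agree with the stated figures (at least 99%, and 90%). The SAP states no power for the TEADA interaction tests.

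**Inputs for the check.** From the documents: n = 184 per arm, SD = 0.88%, three HbA1c visits, alpha 0.10. Assumed, because the documents do not give them: TEADA-positive share p of 10-30%, equal between-visit correlation r = 0.6, and the sizes and time courses of the antibody effect. Complete data are assumed.

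**Formulas.** Let d1, d2, d3 be the treatment-by-TEADA effect at Weeks 4, 8 and 16.
- Variance factor: v = 2 x [1/(np) + 1/(n(1-p))]. At p = 10%, v = 2 x (1/18.4 + 1/165.6) = 0.1208. At p = 30%, v = 2 x (1/55.2 + 1/128.8) = 0.0518.
- 3-way test: chi-square on 2 df, noncentrality = sum of (dk - mean d)^2 / [v x 0.88^2 x (1 - r)].
- Week 16 treatment-by-TEADA contrast: SE = 0.88 x sqrt(v) = 0.306 (p = 10%) or 0.200 (p = 30%).
- TEADA effect at Week 16 averaged over arms: SE is half of that, 0.153 or 0.100.

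**Where the 3-way test has no power beyond alpha.** If d1 = d2 = d3, the numerator is zero. If the TEADA effect is equal in both arms, every dk is zero, even when the effect grows over visits. These results depend on none of the assumed values, and they apply equally to the four-visit dose model.

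**An effect that builds.** For 0.25/0.40/0.50% the mean is 0.383 and the sum of squares is 0.0317. With 0.88^2 x 0.4 = 0.3098, noncentrality is 0.0317/(0.1208 x 0.3098) = 0.85 at p = 10%, and 1.98 at p = 30%. For 0/0.25/0.50% the sum of squares is 0.125, and noncentrality is 3.34 and 7.80.

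| HbA1c effect at Weeks 4/8/16 | 3-way test | Treatment-by-TEADA, Week 16 | TEADA effect, Week 16, averaged over arms |
|---|---|---|---|
| One arm, 0.50/0.50/0.50% | 10% | 50-80% | not the target |
| One arm, 0.25/0.40/0.50% | 20-33% | 50-80% | not the target |
| One arm, 0/0.25/0.50% | 48-80% | 50-80% | not the target |
| Both arms, 0.40% throughout | 10% | 10% | 83-99% |

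Entries are the probability of p<0.10; ranges run from 10% to 30% TEADA-positive.

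**Simulation check.** 4,000 trials per scenario, 30% positive, correlation 0.7. A constant 0.5% effect in one arm was flagged by the 3-way test in 10.3% of trials and by the Week 16 contrast in 80.1%. A 0.5% effect shared by both arms was flagged by the 3-way test in 9.6%, and by the arm-averaged TEADA contrast in more than 99.9%.

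**The case against.** **Other outcomes get a 2-way test.** A reader might infer that the 3-way test is the only antibody check in the plan. It is not. Postprandial glucose, hypoglycemia rate, and the infusion site and hypersensitivity reactions get a 2-way treatment-by-TEADA test, which can show a steady arm-specific effect. But Protocol 9.8 does not name these outcomes as its monitor, and a 2-way test still misses a shared effect.

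**The information is not lost.** A reader might also infer that the trial cannot answer the neutralization question. The documents do not support that. The TEADA models are run whatever the p-value, and SAP 6.1 calls for LS means and standard errors from the analysis models. Estimates by arm, TEADA status and visit can come from the same fit. What is missing is a named contrast with its interval.

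**The 3-way test is not weak for every trajectory.** TEADA arises after Visit 4, so a full effect at Week 4 that then stays flat is an extreme case. For 0/0.25/0.50% the 3-way test matches the Week 16 contrast at correlation 0.6. At 0.7 it is better: 58-90% against 50-80%. This stands.

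**The objective is exploratory and comparative.** The antibody objective compares incidence between arms, Protocol 9.8 regards lispro antibodies as not clinically consequential, and TEADA status is defined after randomization. This limits the weight of a positive-minus-negative difference to a descriptive one. It does not explain why HbA1c by TEADA is tested differently from the subgroups in SAP 6.14.1.

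**Dose has not been quantified.** Basal rates and bolus settings are titrated to glucose targets (Protocol 7.2.1.3 and 7.2.1.4), so a loss of insulin effect may appear in dose rather than HbA1c. No power figure is given for dose; only the zero-noncentrality result carries over.

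**Conclusion.** The point holds for HbA1c and insulin dose. The term that SAP 6.12.7.1 evaluates has power equal to alpha, 10%, for an antibody effect constant over the analysed visits and for any effect shared by both arms. That follows from the definition of the term. For an arm-specific HbA1c effect that builds, the 3-way test ranges from clearly weaker than the Week 16 contrast to equal or better, depending on trajectory and correlation. Those figures rest on the assumed TEADA share, correlation and effect sizes. No planned test or named contrast compares TEADA-positive with TEADA-negative patients on either measure.

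The classification window is a lesser, unquantified point. Visit 801 falls 4 weeks after Visit 13, when study insulin has stopped, so a patient first positive at Visit 801 counts as positive for a Week 16 outcome that came earlier. SAP 6.12.7.1 lists antibody status by visit, so such patients can be identified.

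The change should be made: it is small, and it affects how a null antibody result can be read. It does not touch the primary noninferiority conclusion.

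**What to change.** In SAP 6.12.7.1, for HbA1c and insulin dose by TEADA status:

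1. Evaluate the treatment-by-TEADA interaction at Week 16 (Visit 13), as SAP 6.14.1 does. Keep the 3-way term as supportive if wanted.
2. Report the TEADA-positive minus TEADA-negative difference at Week 16 with a 95% CI, in each arm and averaged over arms, whatever the interaction p-value. Label it descriptive, because TEADA is a post-randomization classification.
3. As a minor point, define TEADA status through Visit 13 for these Week 16 outcomes, and keep Visit 801 for the incidence tables.

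The cost is SAP wording. The models already contain the terms, so this is a choice of contrast and needs no new data. The downsides are that the added difference is a non-randomized association and that a few late positives move to the negative group.
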